#### 4.1.4. Post-baseline PRN Treatment Visit

A *Post-Baseline PRN Treatment visit* is defined as any visit at which a subject received an intravitreal injection of DE-109 (440 µg) in the study eye, or the scheduled Post-Baseline PRN Treatment Visits at Month 2, Month 4, Month 6, Month 8, and Month 10 for subjects under US Amendment 01. Therefore, it is not necessary to receive an injection in a Post-baseline PRN Treatment Visits for subjects under US Amendment 01.

#### 4.1.5. Analysis Visit and Analysis Window

*Analysis visit* is a timing variable to be used for tables and listings involving visits. In SPRING study, possible values of analysis visit include Baseline, Month 2, Month 4, Month 6, Month 8, Month 10, and Month 12. The *analysis window* will be used to determine the analysis visit of an assessment based on the study day of the assessment. The analysis window usually is slightly wider than the corresponding assessment window specified in the protocol for analysis purposes. Table 2 shows the analysis windows for post-baseline visits in SPRING study. Detailed definitions of analysis visit and analysis window will also be provided in the ADaM specifications document.

**Table 2 Analysis Visit and Analysis Window**

Analysis Visit	Visit Window	Analysis Window
Baseline (Day 1)	1	1
Month 2 (Day 60)	[53, 67]	[2, 67]
Month 4 (Day 120)	[113, 127]	[68, 127]
Month 6 (Day 180)	[173, 187]	[128, 187]

Month 8 (Day 240)	[233, 247]	[188, 247]
Month 10 (Day 300)	[293, 307]	[248, 307]
Month 12 (Day 360)	[346, 374]	>=308

In SPRING study, all Post-Baseline Visits including PRN and Unscheduled visits with any study assessments will be mapped to any of the analysis visits according to the table above. For example, an assessment collected at an Unscheduled Visit may be mapped to the analysis visit "Month 4" if the study day of the Unscheduled Visit is 125. Another example, an assessment collected at an Early Termination visit may be mapped to the analysis visit "Month 10" if the study day of the Early Termination visit is 250.

A subject may have more than one visit that is mapped to Month 12. However, only the Month 12 visit with latest date is considered as study exit visit. When summarizing VH and BCVA, Month 12 visit refers to this last Month 12 Visit.

## 4.2. Safety- Related Definitions

### 4.2.1. Study Eye and Fellow Eye

The *study eye* is the eye designated as the study eye in the SAKURA program.

The *fellow eye* is the non-study eye.

### 4.2.2. Baseline Score

For each measure, the *baseline score* of the SPRING study is the observed measurement prior to the injection of DE-109 (440 µg) at Day 1 if an injection is given at Day 1, or the observed measurement by Day 1 otherwise.

### 4.2.3. Change from Baseline

The *change from baseline* in a measure at a post-baseline visit will be derived as:

Change from Baseline at a Post-Baseline Visit = (Score at the Post-Baseline Visit) – (Baseline Score).

For any measure assessed before and after injection at visits, only the pre-injection scores will be used to derive the change-from-baseline variable.

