### 4.2.4. Change after Injection

For any measure assessed before and after injection at injection visits, the *change after injection* at an injection visit will be derived as:

Change after Injection = Post-Injection Score at the Visit – Pre-Injection Score at the Visit.

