**Table 3 Other Safety Assessments**

Safety Measures	Note
Slit-lamp Biomicroscopy: Vitreous haze	VH is assessed for each eye using the modified SUN scale as 0, 0.5+, 1+, 1.5+, 2+, 3+, or 4+. A decrease in VH score

	indicates improvement in the vitreous inflammation.
Best-corrected visual acuity	BCVA measures the acuteness or clearness of best-corrected vision in ETDRS letters (e.g., 75 letters). An increase in BCVA indicates improvement in the best-corrected vision. A 5-letter difference in visual acuity is equivalent to one Snellen line. A BCVA score of 85 ETDRS letters is equivalent to 20/20 vision, which is considered normal vision.
Intraocular pressure (IOP)	IOP, the fluid pressure inside the eye, is recorded in mmHg with one decimal point (e.g., 24.0 mmHg). If DE-109 is administered, a second assessment of IOP is made after injection.
Indirect ophthalmoscopy: lens and cataract	The lens of an eye is classified as Phakic, Aphakic, or Pseudophakic. Phakic lens is assessed for the presence of cataract (Yes or No).
Indirect ophthalmoscopy: Retina, macula, choroid, optic nerve	Retina, macula, choroid, and optic nerve, if able to be assessed, are graded as Normal or Abnormal. If DE-109 is administered, these ophthalmoscopy parameters are performed again after injection.
Slit-lamp biomicroscopy a : Lid Hyperemia, Lid Edema, Conjunctival Hyperemia, Chemosis, Corneal Edema, Conjunctival Discharge Exudate, Anterior Chamber Flare	The status of each of these biomicroscopy parameters is rated as 0 = None, 1 = Mild, 2 = Moderate, or 3 = Severe. For each abnormal record, the clinical significance (Clinically Significant or Not Clinically Significant) is also determined.
Slit-lamp biomicroscopy a : Pupil, Lashes, Ocular Motility, Iris	The status of each of these biomicroscopy parameters is determined as Normal or Abnormal. For each abnormal record, the clinical significance (Clinically Significant or Not Clinically Significant) is also determined.
Slit-lamp biomicroscopy a : Vitreous Cell Count	This measure is rated as 0 = 0 cells, 0.5+ = 1-10 cells, 1+ = 11-20 cells, 2+ = 21-30 cells, 3+ = 31-100 cells, or 4+ = $\geq 100$ cells.
Slit-lamp biomicroscopy a : Anterior Chamber Cell	This measure is rated as 0 = <1 cell, 0.5+ = 1-5 cells, 1+ = 6-15 cells, 2+ = 16-25 cells, 3+ = 26-50 cells, or 4+ = $\geq 50$ cells.

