## **8.4. Intraocular Pressure (IOP)**

IOP, change from baseline in IOP at the Study Exit visit, and change after injection in IOP will be summarized.

Subjects with elevated IOP reported as an AE will be tabulated. Subjects with any increase of  $\geq 10$  mmHg in IOP from baseline at any post-baseline visit, or after injection will be tabulated and listed. In addition, Subjects with IOP of at least 25, 30, or 35 mmHg at any post-baseline visit will be summarized.

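### The SAP's count of IOP rises of 10 mmHg or more tests the pre-injection and post-injection steps separately, so at visits after Day 1 a post-injection reading 10 mmHg or more above baseline can go unflagged

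*SAP*

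**What the plan says.** Four parts of the SAP bear on this.

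- **Baseline (4.2.2).** The baseline score is the "observed measurement prior to the injection of DE-109 (440 µg) at Day 1 if an injection is given at Day 1"; otherwise it is the measurement observed by Day 1.
- **Change from baseline (4.2.3).** For measures taken before and after injection, "only the pre-injection scores will be used to derive the change-from-baseline variable".
- **Change after injection (4.2.4).** "Change after Injection = Post-Injection Score at the Visit – Pre-Injection Score at the Visit".
- **IOP outputs (8.4).** The opening sentence names two separate change quantities: "IOP, change from baseline in IOP at the Study Exit visit, and change after injection in IOP will be summarized". The rise criterion has a threshold of 10 mmHg and covers any such increase in "mmHg in IOP from baseline at any post-baseline visit, or after injection will be tabulated and listed". A separate output uses absolute levels: "Subjects with IOP of at least 25, 30, or 35 mmHg at any post-baseline visit will be summarized". Subjects with elevated IOP reported as an adverse event are also tabulated.

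Protocol 12.2.3 requires an IOP reading before the treatment decision and a second one 40 (±10) minutes after any injection. Protocol 14.6 asks for IOP scores and changes from baseline to be summarized and clinically significant changes listed. It gives no threshold and does not say whether post-injection readings count.

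**The concern.** The 10 mmHg table appears to answer a simple safety question: how many subjects had a pressure reading at least 10 mmHg above where they started? On the defined terms it answers something narrower. A subject whose pressure has moved up by several mmHg before an injection, and moves up again after it, has the total rise split in two. If neither part reaches 10 mmHg, the subject is absent from both the table and the listing.

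Long-term safety is the sole objective of the study, change in IOP is a named analysis parameter (protocol 14.1.1), and a post-injection reading is required at every injection. The data to answer the simple question are therefore collected. With 60 subjects enrolled (SAP 3.3), and if all are in the Safety population, each omitted subject changes the reported percentage by 1/60, or 1.7 points.

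**Working it through.** The plan states no figure for this point, so there is none to reproduce. The check applies the SAP's definitions and finds what they leave out.

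**Inputs**
- Step before injection: a = pre-injection reading − baseline (SAP 4.2.3).
- Step after injection: b = post-injection reading − pre-injection reading, same visit (SAP 4.2.4).
- Flag: a ≥ 10 or b ≥ 10 (SAP 8.4, read through those definitions).
- Precision: 0.1 mmHg (SAP Table 3; protocol 21.4.4).
- Quantity not tested: post-injection reading − baseline = a + b.

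**When a rise is missed.** A visit is missed when a + b ≥ 10 while a ≤ 9.9 and b ≤ 9.9. Both steps must then be positive.

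**Example.** Baseline 12, pre-injection 18, post-injection 24 gives a = 6, b = 6 and a + b = 12. If no other visit is higher, the subject is not flagged for a 10 mmHg rise and has no reading of 25 mmHg or more.

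**Upper bound.** 9.9 + 9.9 = 19.8 mmHg, or 9 + 9 = 18 mmHg if readings are whole numbers.

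**Day 1.** If an injection is given on Day 1, the pre-injection reading is the baseline. Then a = 0 and a + b = b, so the largest unflagged rise is 9.9 mmHg and there is no gap.

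**Do the absolute rows recover these subjects?** Suppose first that the 25/30/35 mmHg rows use post-injection readings. A rise escapes both outputs only if the post-injection reading is at most 24.9. The largest such rise is the smaller of 19.8 and 24.9 − baseline. The baselines below are chosen for illustration.

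| Baseline (mmHg) | Post-injection reading at a 19.8 rise | Largest unflagged rise staying below 25 |
|---|---|---|
| 6 | 25.8 | 18.9 |
| 8 | 27.8 | 16.9 |
| 10 | 29.8 | 14.9 |
| 12 | 31.8 | 12.9 |
| 14 | 33.8 | 10.9 |
| 14.9 | 34.7 | 10.0 |
| 15 | 34.8 | 9.9 (under 10, so no gap) |

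The 19.8 mmHg case therefore reaches the 25 mmHg row from any baseline of 6 or more. Smaller missed rises of at least 10 mmHg escape both outputs for baselines up to 14.9 mmHg (14.9 + 10.0 = 24.9).

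Suppose instead that the rows use pre-injection readings only. Then only baseline + a has to stay at or below 24.9. For a baseline of 15.0, 15.0 + 9.9 = 24.9, so even the full 19.8 mmHg rise would be in neither output for baselines up to 15.0 mmHg. The SAP does not say which applies.

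**After the fix.** With post-injection minus baseline added as a criterion, the largest unflagged post-injection rise over baseline falls from 19.8 to 9.9 mmHg.

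**The case against.** The strongest objection is textual. In the 8.4 sentence, the words *from baseline* can govern both phrases, so that the criterion already means a rise from baseline seen at a visit or after an injection. The restriction in 4.2.3 applies to a named derived variable, and this sentence does not use that name. The reading is possible, but it conflicts with 4.2.3, which keeps post-injection scores out of change from baseline, and with 8.4's own opening, which treats change after injection as a second quantity. At best the rule is ambiguous, and a programmer following the definitions would code the narrower version.

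Second, other outputs may pick up some of these subjects: the absolute rows, elevated IOP reported as an adverse event, and the protocol's listing of clinically significant changes. This stands in part. None of them is a 10 mmHg rise criterion. The adverse-event and clinical-significance routes depend on judgement, and the absolute rows do not state which readings they use.

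Third, keeping sustained change (pre-injection) apart from the acute response (about 40 minutes after injection) is sensible, and a combined measure mixes the two. This stands as a reason to keep both existing criteria as separate rows. It does not justify omitting the combined comparison, because 8.4 already counts acute rises of 10 mmHg or more.

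Fourth, the study is descriptive and no decision rule depends on this count. That limits the consequence but does not remove the gap.

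**Conclusion.** The point holds for injection visits after Day 1. On the SAP's defined terms, a post-injection IOP 10 mmHg or more above baseline can be missing from the 10 mmHg table and listing when each step is below 10 mmHg. This rests on reading 8.4 through 4.2.3 and 4.2.4; if the other reading was intended, 8.4 needs to say so.

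Three stronger conclusions that a reader might draw are not supported:

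- *Post-injection readings are never compared with baseline.* This is wrong for Day 1 injections, where the two comparisons coincide.
- *Rises of almost 20 mmHg would go unseen.* The 19.8 mmHg figure is an arithmetic bound, not an expected value. From a baseline of 6 mmHg or more (protocol 8.2 excludes chronic hypotony below 6), such a rise would show in the 25 mmHg row if that row uses post-injection readings. The firmer statement is that missed rises of at least 10 mmHg can also stay below 25 mmHg for baselines up to 14.9 mmHg.
- *A known share of subjects is missed.* The documents give no IOP means, SDs or correlations. Dosing is as needed, and SAP 7.6 allows for 0 to 6 injections. Any percentage would come entirely from assumed inputs.

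The count is incomplete only as a measure of any reading 10 mmHg above baseline. As a measure of pre-injection change alone, the rule does what it says.

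**What to change.** In SAP 8.4:

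1. Add a table row and listing for subjects with any reading, pre- or post-injection, at any visit after Day 1 that is at least 10 mmHg above the baseline score.
2. Show the two existing criteria as separate rows: pre-injection change from baseline, and same-visit change after injection. The second already covers Day 1 injections.
3. State that the 25/30/35 mmHg rows include post-injection readings.

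Leave 4.2.3 as it is for mean change from baseline.

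The cost is a few words in the SAP, one extra row and one listing, all from data already collected. The reported count may be less favourable and will include transient post-injection readings, which the separate rows allow a reader to identify.

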### 4.2.4. Change after Injection

For any measure assessed before and after injection at injection visits, the *change after injection* at an injection visit will be derived as:

Change after Injection = Post-Injection Score at the Visit – Pre-Injection Score at the Visit.

## 4.3. Efficacy Related Definitions

The long-term efficacy of DE-109 (440 µg) may be explored by VH. There are no efficacy-related endpoints that need to be defined in this document.

## 4.4. Safety Related Definitions

### 4.4.1. Adverse Event

Under Protocol 32-009, an AE is defined as any *on-study* untoward medical occurrence (e.g. sign, symptom, disease, syndrome, intercurrent illness) that occurs in a study subject, regardless of the suspected cause and regardless of timing of DE-109 (440 µg) administration. An on-study AE can occur any time after the date of informed consent through the last study visit. An AE will be considered as *treatment-emergent* if the AE occurred on or after the date of the first DE-109 (440 µg) treatment in Spring Study up to the last study visit. Treatment-emergent AEs are a subset of on-study AEs.

The severity of each AE will be graded by the Clinical Investigator as Mild (aware or unaware of event, but easily tolerated), Moderate (discomfort enough to cause interference with usual activity), or Severe (incapacitating; unable to work or perform usual activity). Each AE will be classified into a system organ classification (SOC) and coded to a preferred term using Medical Dictionary for Regulatory Activities (MedDRA 16.0).

#### 4.4.1.1. Ocular Adverse Event

An AE will be counted as an *ocular AE* if the Clinical Investigator selected 'OD', 'OS', or 'OU' under Item 2 (Eye(s) affected) on the AE eCRF.

#### 4.4.1.2. Serious Adverse Event

Serious Adverse Events (SAEs) are defined as any findings that suggest a significant hazard, contraindication, side effect, or precaution. An AE will be counted as a *serious adverse event* (SAE) if the Clinical Investigator selected 'Yes' under Item 5 (Is the adverse event serious?) on the AE eCRF. Any adverse event is considered a serious adverse event if it results in any of the following outcomes:

- Death;
- Life threatening:  
A life-threatening event is any event that places the subject at immediate risk of death from the event as it occurred; it does not refer to an event that hypothetically might have caused death if it were more severe;
- In-subject hospitalization and/or prolonged hospitalization;
- A persistent or significant disability/incapacity;
- A congenital anomaly/birth defect;
- Sight threatening event

A *sight-threatening AE* is defined as any ocular AE that places the subject at immediate risk of permanent vision loss in either the study eye or the fellow eye. See more in Section 4.4.1.2.1;

- Other medically significant events:

Other medically significant events are events that may not result in death, be life-threatening, or require hospitalization but may be considered a serious adverse drug experience when, based upon appropriate medical judgment, they may jeopardize the subject and may require medical or surgical intervention to prevent one of the outcomes listed above.

#### 4.4.1.2.1. Sight-Threatening Adverse Event

The *sight-threatening AE* is defined as any ocular AE that places the subject at immediate risk of permanent vision loss in either the study eye or the fellow eye. In this extension study, the following serious ocular AEs will be reported as sight-threatening AEs:

- Loss of 6 or more lines of vision ( $\geq 30$  letters) from Baseline;
- Endophthalmitis;
- Purulent, infectious conjunctivitis;
- Retinal detachment;
- IOP  $> 35$  mmHg that persists for at least 7 days despite pharmacologic therapy;
- Other significant ocular events per Investigator's discretion.

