### **12.1.3. Sight Threatening Events**

For the purposes of this study the following ocular adverse events will be reported as serious adverse events:

- Loss of 6 or more lines of vision ( $\geq 30$  letters) from Baseline;
- Endophthalmitis;
- Purulent, infectious conjunctivitis;
- Retinal detachment;
- IOP  $> 35$  mmHg that persists for at least 7 days despite pharmacologic therapy;
- Other significant ocular events per Investigator's discretion

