## **8.3. Best-Corrected Visual Acuity (BCVA)**

BCVA and change from baseline in BCVA at Month 12 and Study Exit visit will be summarized and listed.

Subjects with improvement or worsening of at least 5 letters, 10 letters, or 15 letters in study eye at Month 12 visit will be tabulated, as well as subjects maintained BCVA within 5 letters of change in study eye.

Subjects with any BCVA score of 0 after baseline will be listed.

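### The SAP does not settle whether a listed sight-threatening event not marked serious is counted, and a recovered loss of 30 or more letters appears in no planned BCVA output

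*SAP*

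**What the plan says.** **Protocol.** Section 12.1.3 states that "the following ocular adverse events will be reported as serious adverse events". The list has six items: loss of 30 or more letters from baseline, endophthalmitis, purulent infectious conjunctivitis, retinal detachment, persistent IOP above 35 mmHg, and other significant ocular events at the investigator's discretion. Section 14.6 says that clinically significant changes from baseline in BCVA, among other ocular measures, will be listed.

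**SAP, seriousness.** Section 4.4.1.2.1 carries the same six items but introduces them with "the following serious ocular AEs will be reported as sight-threatening AEs". Section 4.4.1.2 counts an AE as serious "if the Clinical Investigator selected 'Yes' under Item 5" of the AE form. The same paragraph goes on: "Any adverse event is considered a serious adverse event if it results in any of the following outcomes", and a sight-threatening event is one of those outcomes. Both sections define a sight-threatening AE in general terms as "any ocular AE that places the subject at immediate risk of permanent vision loss", in either eye, with no condition on seriousness. Section 8.1 summarises sight-threatening AEs by the event types in 4.4.1.2.1.

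**SAP, visual acuity.** Section 8.3 summarises and lists BCVA and its change from baseline at Month 12 and Study Exit. It tabulates subjects with "improvement or worsening of at least 5 letters, 10 letters, or 15 letters in study eye at Month 12 visit", and lists any subject with a score of 0 after baseline.

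**The concern.** In the protocol, being on the list makes an event serious. The SAP's introductory sentence can be read the other way round, with seriousness as an entry condition for the list. Item 5 is the only data field the SAP names for counting SAEs. It fixes other AE flags in the same manner (Item 2 for ocular events, Items 11 and 12 for suspected reactions), so a programmer could reasonably build the SAE flag from Item 5 alone and the sight-threatening flag from within it. A retinal detachment left unmarked at Item 5 might then be missing from both summaries.

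Long-term safety is the study's only objective, and sight-threatening events are among its gravest ocular harms. In about 60 subjects, the difference between none and one matters to a reader of the report. One listed event, the 30-letter loss, can also be derived from measured BCVA without relying on any investigator's tick, so it is worth asking whether the planned BCVA outputs would catch it.

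**Working it through.** Neither document states a figure on this point, so there is none to reproduce. The check is a comparison of text, followed by an illustration of scale.

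**1. One event under the SAP's own sentences.** Take a retinal detachment recorded as an ocular AE with Item 5 not answered Yes.

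| Reading of SAP 4.4.1.2 and 4.4.1.2.1 | SAE table | Sight-threatening summary |
|---|---|---|
| Item 5 governs; the word serious is a condition | not counted | not counted |
| Outcome criterion governs; the word serious is descriptive | counted | counted |
| Item 5 governs SAEs; the general definition governs sight-threatening AEs | not counted | counted |

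The text permits all three results, and the SAP has no rule for a conflict.

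**2. Direction of any error.** Let L be the listed events and T the events with Item 5 answered Yes. The literal rule counts L ∩ T; the protocol's rule counts L. Since L ∩ T is contained in L, the literal rule can lower the count and never raise it.

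**3. Where an uncounted event would still show.** SAP 8.1 tabulates all subjects with AEs by system organ class, preferred term and maximum severity, summarises ocular AEs, and lists every AE. SAP 8.4 summarises IOP of at least 25, 30 or 35 mmHg at any post-baseline visit, though not persistence for 7 days. SAP 8.3, with SAP 6 (minimum and maximum) and SAP 8 (study and fellow eyes separately), would show a 30-letter loss present at Month 12 or Study Exit in the change listing, and the largest loss as the minimum change. In the study eye at Month 12 it also falls in the category of at least 15 letters, which has no upper limit.

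**4. Where a 30-letter loss would not show.** BCVA is measured in each eye at Day 1, Month 12 and PRN treatment visits (Protocol 12.2.2), and also at scheduled Month 2 to 10 visits for subjects under US Amendment 01 (SAP Table 1), who number 13 of 60 (SAP 3.3). Apart from the listing of scores of 0, the outputs in SAP 8.3 use Month 12 and Study Exit only. Consider a subject with a baseline of 85 letters, 55 at an intermediate visit and recovery by exit:

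- Loss at the intermediate visit: 85 − 55 = 30 letters, which meets the listed criterion.
- Score at that visit: 55, so the score-of-0 listing is not triggered. A loss of exactly 30 letters gives a score of 0 only when the baseline is 30.
- Month 12 and Study Exit: recovered, so nothing appears.

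If the site recorded an AE, the AE outputs show it. If it did not, no planned AE or BCVA output does. SAP 8.3 contains no listing matching the one in Protocol 14.6.

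**5. Scale.** Inputs: n = 60 (SAP 3.3), and an assumed 0 to 3 subjects with a listed event. One missed subject lowers the rate by 1/60 = 1.67 percentage points. The exact (Clopper-Pearson) 95% limits are the 2.5% quantile of Beta(x, n − x + 1) and the 97.5% quantile of Beta(x + 1, n − x), with a lower limit of 0 when x = 0.

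| x / 60 | Rate | Exact 95% CI |
|---|---|---|
| 0 | 0% | 0 to 5.96% |
| 1 | 1.67% | 0.04 to 8.94% |
| 2 | 3.33% | 0.41 to 11.53% |
| 3 | 5.00% | 1.04 to 13.92% |

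**The case against.** The strongest reply is that the SAP already says what the protocol says. The sentence after the Item 5 rule makes any sight-threatening event serious, and the general definition covers any ocular AE with that risk. If every such event is serious by definition, the word in 4.4.1.2.1 merely describes the list. This is a fair reading. A reader might infer that the SAP counts listed events only once they are marked serious, and that an unmarked one drops out of both tables. The documents do not support that as a settled rule; it is the first of the three readings above.

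A reader might also infer that no output would reveal a missed event. That is wrong: the AE tables and listings, the IOP thresholds, and the BCVA change summaries and listings would show many of them.

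The harm also needs several failures together: a site departing from Protocol 12.1.3, monitoring (Protocol 15.1) and eCRF review (Protocol 16.1 and 18.2.2) not catching it, and programming that ignores the outcome criterion. This stands as a reason to expect few cases. Finally, forcing SAE status in analysis whatever the form says would make tables disagree with the database. That stands too, and the remedy should be a query.

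Two things remain. The SAP gives two criteria without saying which one prevails, and the recovered 30-letter loss stays outside the BCVA outputs even when Item 5 is always completed correctly.

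**Conclusion.** The concern holds as an ambiguity with a one-sided risk, plus one specific gap in the BCVA outputs. The documents do not show that sight-threatening events will be undercounted. They give no rate of unmarked events, so the effect cannot be estimated, and 1/60 against 0/60 only illustrates what one missed subject would do. The plan is descriptive and calls for no confidence intervals; those above are for scale.

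Assumptions: all 60 subjects enter the Safety population, and the listing in SAP 8.3 is confined to the visits it names. The SAP says it applies to US Amendment 01, whereas the protocol text reviewed has no scheduled Month 2 to 10 visits; I assume that Protocol 12.1.3 and 14.6 read the same in the amendment. The change is an inexpensive improvement worth making before database lock.

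**What to change.** - **SAP 4.4.1.2.1:** delete the word serious from the introductory sentence. Build the sight-threatening flag from the list regardless of Item 5. The last item, other significant ocular events, still needs the investigator's judgement and cannot be derived.
- **SAP 4.4.1.2:** state which criterion governs the SAE tables. Query every listed event with Item 5 not answered Yes before database lock, so that the site corrects or confirms the record, and do not override the eCRF in analysis.
- **SAP 8.3:** derive a loss of at least 30 letters from baseline at any post-baseline visit, tabulate it for study and fellow eyes separately, and list cases with no matching AE. Add the listing of clinically significant BCVA changes from Protocol 14.6, with its threshold stated.

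The cost is a few SAP sentences, one derived flag and some site queries. No new data are needed. The reported count may be slightly higher.
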